5.1 Sampling Strategy

The inclusion criteria for a household to be eligible for the study was that, at the start of the study in 2013:

1. The household resided in Gulbarga or Mysore district;
2. The household resided within 25 km of a hospital empaneled in RSBY; and
3. A member of the household must hold an Above Poverty Line (APL) ration card.

The exclusion criteria for the study were:

⁶They can be found at <http://www.rsbyp.gov.in/Documents.aspx?ID=4>

1. The possession of a BPL card;
2. Having a member working in one of the occupations that made the household eligible for RSBY regardless of BPL status; or
3. Having insurance that covered secondary hospital care (most commonly, Yeshasvini).

The two districts we selected were representative of central and southern India, respectively. We focused on APL households because they were treatment naive: they were not otherwise eligible for RSBY. The set of all household that met these inclusion criteria was larger than the target sample size for the study. Therefore we restricted enrollment to 25 km around a subset of hospitals in each district. We also omitted villages with ≤ 10 eligible households as the amortized fixed costs of reaching those households were very high.

The RCT was powered to detect a 25% change in hospitalization rate across study arms, allowing for a 10% attrition rate.

5.2 Treatment assignment

We designed a two-stage randomization process to study both direct treatment and spillover effects of health insurance.

In a first stage, we randomly assigned villages to one of five village-level arms. A village-level arm is defined by the percentage of households within the village assigned to each of the four household-level study arms defined in subsection 4.2.1. The percentage allocations to the 4 household-level arms are given in the last 4 columns of Table 1. The percent of villages assigned to each of the 5 village-level arms are in the second column. Villages were matched before this first stage randomization.⁷

Table 1: IHIE Two-Stage Randomization Design

Village-level arms (%)		Household-level arms (%)			
Arm	Village allocation	Group A	Group B	Group C	Group D
I	15	30	50	10	10
II	15	30	10	50	10
III	15	30	10	10	50
IV	35	70	10	10	10
V	20	10	30	30	30
Total	100	40	20	20	20

In a second stage, we randomly assigned households within a village to the four arms according to the allocation probabilities assigned to the village. Households were matched before this second stage randomization.⁸

The target enrollment for each of the 4 household-level arms, unconditional on village-level arm, was 4,500 households for condition A and 2,250 households for each of conditions B, C and D. Due to some attrition between listing and completion of baseline, our final randomized sample amounted to 11,089 households in 424 villages in the two districts.

5.3 Data Collection

We conducted 6 rounds of data gathering: (1) a listing exercise; (2) a baseline survey; (3) an enrollment survey; (4) a 12 month follow-up survey, which uses a novel design we call a Post-Health Event Survey

⁷Specifically, we first stratified villages into quintiles of: # eligible hhds per village. Within each quintile, we created blocks of 20 villages. Using data from our listing exercise on average values for certain variables (among eligible hhds in a village), create blocks as follows:

- Mahalanobis matching on: education, age of household head, # children, # rooms in house
- Caliper matching on binary variables: major illness, unemployment in household

Within a village block, we randomly assign villages to 5 village-level conditions (without replacement).

⁸Specifically, within each village, we first created blocks of 10 eligible and consented households. Using household-level data from listing survey, create blocks as follows:

- Mahalanobis matching on: education, age of household head, # children, # rooms
- Caliper matching on binary variables: major illness, unemployment in household

Within each block of households, we randomly allocate households to the 4 household-level conditions in accordance with the village-level assignment probability condition (without replacement).

(PHES); (5) an 18 month follow-up survey, which we label a midline survey; and (6) a 4 year follow-up survey, which we call an endline.

5.3.1 Listing

In March – June 2013 and again in November - December 2013, we conducted listing exercises to identify candidate villages and households. This round also gathered variables that we used for randomization. Only 1 adult in each household was interviewed.

5.3.2 Baseline Survey

The baseline survey took place in August 2013 – February 2014. This round included a consent form for the overall study as well as the survey. We administered surveys to up to 3 distinct members of each household (the female and male most knowledgeable about household finances and a female of childbearing age) for the entire sample. These individuals were asked modules about subjective health status, health care consumption and financial status. In addition, for a subsample of roughly 4000 households, we also conducted an anthropometric survey that gathered objective health status (e.g., BP, body fat, weight, lung capacity), on up to 3 members of the household (the male most knowledgeable about household affairs, a female with childbearing capacity, and a child under the age of 5. Households were paid INR 250 as a participation incentive for completing major sections of the survey. We performed back checks on 10% of households, a rate known to surveyors *ex ante*.

5.3.3 Enrollment Survey

A short enrollment survey was conducted during May and June 2015 when households were told their household-level treatment assignment. All households were surveyed, although response rates were lower than other survey rounds because this enrollment survey was not prioritized during the enrollment process.

5.3.4 Post-health Event Survey (PHES)

In May and June 2016, we conducted a 12 month follow-up. We used a different survey design, the PHES. Instead of surveying all households, most of whom may not have had a sickness that required treatment covered by insurance, we only surveyed those households that reported (via a phone interview) a serious sickness. Moreover, we only asked households about sicknesses and treatment in the 2 months prior to the phone screening call. These two design decisions were intended to reduce survey costs and reduce recall bias, respectively. Only 1 member of the household was surveyed. Screening questions and survey questions for PHES were asked to the head of the household or to the most knowledgeable person (from roster). Respondents were asked about the previously identified health event, treatment, and finances.

5.3.5 Midline Survey

In November 2016 – February 2017, we conducted an 18 month follow-up survey. The format was nearly identical to the baseline survey, including the anthropometric survey. Households were paid INR 250 as a participation incentive for completing major sections of the survey. We performed backchecks on approximately 15% of households,⁹ a rate known to surveyors *ex ante*.

5.3.6 Endline Survey

In March - May 2019, we will be conducting a 4 year follow-up survey. We will survey 1 member (our first priority is to interview the female most knowledgeable from baseline (or midline for households with missing baseline data), followed by the current female most knowledgeable, and then the male most knowledgeable) of each household in the sample. Respondents will be asked about subjective health status, health care consumption and financial status. Households will be paid a participation incentive comprised of bars of soap and tubes of toothpaste valued at approximately INR 50 for completing major sections of the survey. We will perform backchecks on 10% of households, a rate known to surveyors *ex ante*.

Rounds (1) – (3) were conducted on paper and the remainder on tablets. Rounds (1) – (4) were conducted by IFMR and the midline (5) by Nielsen. The endline will be conducted by Outline India.

⁹The actual rate is 4 households per village on each module of the the survey.

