7.5 Minimizing attrition bias

We address the possibility that attrition affects our ITT or CATE estimates in the following manner. Let a_{ijk} be an indicator that equals 1 if our data contain a non-missing observation on household i in village j at baseline but not at endline. First, we check balance in attrition across household or village treatment arms by estimating the ITT model in equation (2) while setting $y_{ijt} = a_{ij}$. We will also test whether there is differential attrition across insured and uninsured households by estimating system (3) while setting $y_{ijt} = a_{ij}$.

Second, if we find evidence of differential attrition, we will take either of two approaches. One is to impute outcomes for attrited households using multiple imputation (King et al. 2001). In this approach, we will compare ITT and CATE effects with imputation and without. The other approach is to bound our parameter of interest using Lee bounds (Lee, 2009).

If we observe differential attrition, we will estimate all of our regressions with a correction for sample selection inspired by DiNardo, Fortin, and Lemieux (1996). Their procedure re-weights the data using the inverse of the propensity to be observed at endline, so that the distribution of observable characteristics at baseline among households observed at endline resembles that in the entire baseline sample.

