8.4 Health value

- Sickness (as defined in PHES)
- Pregnancy or stillbirth (as defined in PHES)
- Self-reported health rating (1 to 5)
- Mortality (all cause and sickness-associated)
- Weight

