8.4.4 Mental and emotional health and cognitive function

- GHQ-12 (to measure depression)
- PSS-10 (to measure stress)

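### Endline replacement of the baseline-designated woman is invisible to the household-level attrition check, so self-reported health scores could be biased by arm without the plan detecting it

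*Combined protocol and SAP*

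**What the plan says.** Section 5.3.6 sets the endline respondent rule: "We will survey 1 member" of each household. The order starts with "our first priority is to interview the female most knowledgeable from baseline" (from midline where baseline data are missing), "followed by the current female most knowledgeable, and then the male most knowledgeable". It does not say what triggers a move down the list. It adds: "Respondents will be asked about subjective health status, health care consumption and financial status".

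Section 7.5 sets the attrition indicator to 1 when "our data contain a non-missing observation on household i in village j at baseline but not at endline". The test by arm uses this indicator. Imputation, Lee bounds and re-weighting follow only if differential attrition is found, and the re-weighting is defined on households seen at endline.

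Sections 8.4, 8.4.3 and 8.4.4 list self-rated health, SF-8, physical symptoms, GHQ-12 and PSS-10 as outcomes. Section 8.4 lists mortality separately. Section 8.5 lists the respondent's gender, age and household role among variables that may serve as controls.

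**The concern.** The self-report scales describe whoever answers them. A footnote in Section 8.5 supports this reading: enumerators were told to ask the health questions with nobody else present. When a substitute answers, the household's score comes from another person, possibly of different age and sex, and the attrition indicator stays at 0.

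Who answers is settled after randomisation. If insurance changes survival, health or availability, the mix of original and substitute respondents may differ by arm, and the ITT on these scales would no longer compare like with like. The scales bear on evaluation questions 1(b) and 1(c) in Section 3, on health and peace of mind, and they would feed the group indices of Section 7.4.

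A second issue concerns households with missing baseline data. Their designated woman is taken from the midline (November 2016 to February 2017), after treatment was delivered in May and June 2015, so her designation is itself post-treatment.

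**Working it through.** **1. What the planned check registers.** A household present at baseline and answered for by a substitute at endline has an attrition indicator of 0. This is so at any replacement rate. It adds nothing to the test by arm, and no imputation, bound or weight treats it as missing.

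**2. What the plan gives.** There is no figure for respondent replacement. The nearest is household attrition to midline, stated as 7%; from 10,111 of 11,089 households, 1 − 10,111/11,089 = 8.8%. That mismatch is a separate matter and does not enter below.

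**3. Bias formula.** Let s be the share of households with a substitute and g the score gap in SD (substitute minus designated woman, positive meaning healthier). Then

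bias (A − D) = s_A·g_A − s_D·g_D, which is (s_A − s_D)·g when the gaps are equal.

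Both s and g are assumptions.

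| Assumed difference s_D − s_A | Gap 0.5 SD | Gap 1.0 SD |
|---|---|---|
| 0 | 0 | 0 |
| 0.5 point | −0.0025 | −0.005 |
| 1 point | −0.005 | −0.01 |
| 2 points | −0.01 | −0.02 |

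The sign shown is for more replacement in D by healthier people, which works against insurance. Unequal gaps have the same effect without any difference in rates: 2% replaced in both arms, with gaps of 0.5 SD in A and 1.0 SD in D, gives 0.02 × (0.5 − 1.0) = −0.01 SD.

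**4. Standard error for A v D, in SD units.**
- Target sizes in Section 5.2: √(1/4,500 + 1/2,250) = 0.0258.
- 11,089 households split 40/20 with 10% attrition, i.e. 3,992 v 1,996: √(1/3,992 + 1/1,996) = 0.0274.
- The latter with an assumed design effect of 2: √2 × 0.0274 = 0.0388.

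**5. Bias relative to the standard error.** For a difference of 0.5 to 1 point: 0.0025/0.0258 = 0.10 to 0.01/0.0258 = 0.39, or 0.09 to 0.36 with 0.0274.

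**6. Effect on power.** For a true effect that would have 80% power, power becomes Φ(0.84 − bias/SE). Unclustered (0.0274), a bias of 0.0025 to 0.01 SD leaves about 77% to 68%. With a design effect of 2 it leaves about 78% to 72%.

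**7. Would a respondent-level indicator help?** For A v D, two-sided 5%, clustering ignored, power to detect a difference in replacement is about 44% for 5% v 4%, 96% for 5% v 3%, and 73% for 10% v 8%. It would find a 2-point difference fairly reliably, but a null result would not exclude a 1-point one.

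**8. Period that can reflect insurance.** From May–June 2015 to March–May 2019 is 45 to 48 months. Losses between baseline and treatment delivery cannot be effects of insurance.

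**The case against.** The strongest reply is that the rule is the same in every arm. Equal replacement with equal gaps shifts score levels but not the contrast between arms, and nothing in the documents shows unequal replacement. This stands: the bias is conditional.

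It can also be said that the plan already holds the relevant data, since respondent age, gender and role are recorded. This stands only in part. Their use is optional, no continuity check is committed to, and they are measured at endline, so adjusting for them conditions on a post-randomisation event.

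A reader might infer more than the text supports:
- *That the worst health outcomes are replaced by a healthier person's scores.* No trigger for fallback is given. Absence, moving or a change of role may explain much of it, and that the substitute is healthier is an inference. Deaths are kept as a separate outcome, and utilization, finance and assets do not become another person's score because another knowledgeable member reports them.
- *That arm D's scores are inflated.* This needs more replacement in D, or a larger gap there. Neither is shown.
- *That the bias is about the size of the standard error.* That takes a gap near 3 SD: 0.005 × 3 = 0.015 to 0.01 × 3 = 0.03 SD, or 0.6 to 1.2 standard errors. The documents give no basis for such a gap, and for a deceased woman, who has no score, it amounts to choosing a penalty for death.
- *That all 61 to 69 months from baseline to endline count.* Only the 45 to 48 months after treatment delivery can reflect insurance.

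**Conclusion.** The gap is real but limited in scope. For outcomes that describe the respondent, the plan permits substitution, counts the household as fully observed, and has no committed step that would show whether substitution differs by arm. Mortality and household-level outcomes are not affected in this way.

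The size cannot be known from the documents. Under the assumed 0.5 to 1 point difference and 0.5 to 1.0 SD gap, the bias is roughly a tenth to four tenths of the unclustered standard error. It is zero under equal replacement and equal gaps, and larger if the difference reaches 2 points. If insurance averts death or serious illness and substitutes are healthier, it would run against insurance; for absence or change of role the direction is open. The case for change is that the plan could not tell a negligible bias from a material one, and that a check is cheap.

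**What to change.** In Section 7.5, for the respondent-level outcomes only:

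1. Define an indicator that the baseline-designated woman was not herself the endline respondent, by matching recorded respondent age, gender and role to the baseline roster. Fieldwork had to identify her in order to ask for her first, so a match should be feasible, with some misclassification.
2. Test it by arm with equation (2), beside the household indicator, and report the estimated differences with intervals, since power against a 1-point difference is modest.
3. Where it differs by arm, apply the planned imputation, bounds or re-weighting to these outcomes using this indicator.
4. In all cases report a same-person ITT as a sensitivity analysis beside the any-respondent ITT, because unequal gaps would not show in the rates. Adjust for the designated woman's baseline age, and for her baseline score where the scale was measured then. State that this analysis is itself selected on survival and availability.
5. If recorded deaths can be linked to the designated woman, add a sensitivity analysis that ranks deceased women worst.
6. Flag households whose designation comes from the midline.

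The cost is plan wording, analysis time and a smaller same-person sample. Splitting replacement into death, illness and absence would be informative, but the documents do not say that reasons were recorded. Fieldwork was scheduled for March to May 2019 and this version is dated June 24, 2019, so reasons not collected may be unrecoverable. The split should be made only if the data exist.

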5.4 Treatment Delivery

The population that is eligible for this study would not be eligible for RSBY under the program's usual rules. To make this study possible, we exchanged letters of cooperation with the state in which we conducted the study (Karnataka), the central government agency (Ministry of Labor) responsible for administration of RSBY, and the development organization (GIZ) providing technical support for RSBY.

Sample households were randomized in August 2014 using data from the listing exercise. They were informed of their treatment assignment and, depending on which arm to which they are assigned, given access to insurance or cash in May and June 2015. This step took place roughly 18 months after the baseline due to government constraints. Due to challenges associated with evaluating a government program, we were only able to enroll sample households when the government held its RSBY enrollment drive in early 2015.

We enrolled study households much in the same way the government enrolled RSBY (non-study) eligible households into the program: via a mobile enrollment truck that visited each village. One difference is that we went to each household to ask them if they would like to enroll and took them to the enrollment truck, which was parked in one place in the village. By contrast, the government informed non-study households by delivering paper notices (chits) to each home about when and where the enrollment truck would be in the village.

Roughly 78.4%, 70.4% and 58.6% of households in arms A, B, and C, respectively enrolled in RSBY. Enrollment rates are somewhat higher in Gulbarga than Mysore: 77.9/76.4/64.1% v. 78.8/63.5/52.3% in A/B/C. No one in arm D enrolled.

For all study households that take up insurance, we paid the government their premiums. For households in arms A, this was funded by grant funds. For those in B and C that purchase insurance, this was funded by the respondents' money.

The Karnataka government renewed RSBY automatically for non-study and study households in 2016 and 2017 without any action—even payment—by enrollees. RSBY ended in the state on August 31, 2018, to make way for the new NHPS scheme, which is scheduled to start in late 2018 or early 2019. As of this writing, Karnataka had agreed to roll out NHPS but had not begun the roll-out.

5.5 Balance Tests

We conduct balance tests to validate that assignment to treatment was indeed random. We do this in 5 steps.

1. We gather baseline measurements on a subset of important outcome variables (defined in section 8).
2. We estimate multinomial logit models predicting household treatment assignments for each household (A/B/C/D) as a function of outcomes measured at baseline, one outcome at a time.
3. We conduct likelihood ratio tests where the null model is the same multinomial model without the baseline covariate, to determine if we can reject the null that these two models are statistically equivalent, i.e., that the baseline covariate has no explanatory power. We collect the p-value from these LR tests.
4. If the randomization is successful, then the *p*-values from these tests should stochastically dominate the uniform distribution. We will use the one-sided Kolmogorov–Smirnov test to determine if this expectation is supported by the data.

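### The only stated criterion for random assignment in section 5.5, one Kolmogorov–Smirnov test over many p-values, rarely detects a gross baseline imbalance confined to one outcome

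*Combined protocol and SAP*

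**What the plan says.** Section 5.5 states its purpose: "We conduct balance tests to validate that assignment to treatment was indeed random". It takes baseline values of a selected subset of the section 8 outcomes, without saying which or how many. It models household arm (A/B/C/D) "as a function of outcomes measured at baseline, one outcome at a time" and compares each model with its null model by an LR test. It then says: "We collect the p-value from these LR tests". Under successful randomisation the p-"values from these tests should stochastically dominate the uniform distribution". The decision step is a one-sided Kolmogorov–Smirnov "test to determine if this expectation is supported by the data".

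The section gives no significance level, no per-outcome threshold, no standardised differences and no consequence of finding an imbalance. It announces five steps and lists four.

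Section 7.1 estimates the ITT models first without controls and then with baseline controls chosen by machine learning. Nothing there requires the baseline value of the outcome being analysed to be among them.

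**The concern.** Each ITT estimate depends on balance in its own outcome and in the variables that predict it. The KS statistic is the largest gap between the empirical distribution of the p-values and the uniform line. With k p-values, one value at zero raises the empirical distribution by only 1/k, however extreme the imbalance behind it. A clear baseline difference in, say, hospital use or medical spending could therefore sit behind a reassuring global result. The estimate without controls for that outcome would then be read with more confidence than the data justify. The information needed to see the difference is already produced in step 3, but the plan gives no rule for using it.

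**Working it through.** The plan gives no power or error rate for this check, so there is no figure of its own to reproduce.

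**Inputs from the documents**
- "our final randomized sample amounted to 11,089 households in 424 villages in the two districts" (section 5.2), so N = 11,089.
- Arm allocation 40:20:20:20, the Total row of Table 1.
- LR test on 3 degrees of freedom: four arms, one scalar covariate.

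**Assumptions**
- Significance level 0.05, with 0.10 also tried.
- k = 5 to 150 outcomes, independent unless stated.
- The one-sided KS test looks for too many small p-values.

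**Step 1: the outcome's own LR test.** If one 20% arm is shifted by d SD, the noncentrality is N × 0.20 × 0.80 × d² = 11,089 × 0.16 × d² = 1,774 d².

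| d (SD) | Noncentrality | Power, level 0.05 (cut-off 7.81) | Power, Bonferroni over 20 (level 0.0025, cut-off 14.32) |
|---|---|---|---|
| 0.1 | 17.7 | 96% | 75% |
| 0.15 | 39.9 | >99% | 99.7% |
| 0.2 | 71.0 | 100% | 100% |
| 0.5 | 443.6 | 100% | 100% |

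Hochberg has at least the power of Bonferroni. If clustering halved the information, the last column would read 31%, 82%, 99% and 100%. For an outcome measured only in the anthropometric subsample of about 4,000 households (section 5.3.2), the unadjusted power is 55% at 0.1 SD and 99% at 0.2 SD.

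**Step 2: the KS test.** D+ = max(i/k − p₍ᵢ₎) is compared with its exact 5% critical value. One p-value is near zero and the other k − 1 are uniform. Results are from simulation.

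| k | Critical value | Missed, one outcome imbalanced | Missed, three imbalanced |
|---|---|---|---|
| 5 | 0.509 | 87% | 0% |
| 10 | 0.369 | 90% | 55% |
| 20 | 0.265 | 92% | 77% |
| 30 | 0.218 | 92% | 82% |
| 50 | 0.170 | 93% | 87% |
| 150 | 0.099 | 94% | 91% |

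With no imbalance at all, non-rejection is 95%. At k = 20, one gross imbalance therefore moves it only from 95% to 92%. Rejection at k = 20 is certain only from six near-zero p-values, because 5/20 = 0.25 is below 0.265 and 6/20 = 0.30 is above it. The size of the imbalance hardly matters: at k = 10 the rejection rate is 9.9% at 0.1 SD and 10.0% at 0.5 SD. A direct check with fitted multinomial logits (N = 11,089, k = 20, 0.5 SD) rejected in 4 of 60 replicates, or 6.7%.

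**Step 3: sensitivity, one outcome imbalanced**
- Level 0.10: missed 77% (k = 5), 82% (10), 84% (20) and 87% (50).
- Correlated outcomes, k = 10 to 50, level 0.05: missed 89–90% at correlation 0.1, 78–85% at 0.3 and 70–79% at 0.5. Most of the extra rejections are false. With no imbalance the test rejects 10–20% of the time at 0.3 and 17–29% at 0.5.
- If matching before randomisation shrinks the LR statistics by 5% to 20% (k = 10 to 50): missed 93% to 99.9%.

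**Step 4: can the LR p-values be used as they stand?** Arm shares differ between village groups (Table 1), so an LR test that ignores villages is too liberal when outcomes cluster. With 424 villages of 26 households (11,089/424 ≈ 26), Bonferroni over 20 null outcomes gave at least one false flag about 13% of the time at an assumed intraclass correlation of 0.05 and about 29% at 0.10. That is roughly 20% across that range.

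**The case against.** The strongest reply is about purpose. Section 5.5 asks whether the assignment mechanism was random, which is a global null, and an omnibus test of the p-value distribution fits that question. A real failure of assignment would probably move several related outcomes together, and KS does better there: with three of ten imbalanced it misses 55% rather than 90%. This stands, and it is why KS is worth keeping. But with three of 20 imbalanced it still misses about three times in four.

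A reader might infer that the plan treats a non-significant KS result as proof that every outcome is balanced. It does not say so. It says only that the test decides whether the expectation of randomness is supported. Nor can it be said that the plan is unable to see a single imbalance, because step 3 yields a p-value for each outcome. The missing fifth step might even have held a rule for them, but the text has none.

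A reader might also infer that selective loss between randomisation and baseline, which section 5.6.1 mentions, could produce such an imbalance. The dates do not support that. Baseline ran from August 2013 to February 2014 (section 5.3.2). Households were randomised in August 2014 and told their arm in May and June 2015 (section 5.4), so baseline response could not have depended on arm. Later loss does not change a comparison across the baseline sample, and section 7.5 handles endline attrition separately.

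Finally, no analysis is conditional on the section 5.5 result, and the controlled models are run regardless. That limits the harm. It does not remove it, because the machine-learning selection may leave out the outcome's own baseline value.

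**Conclusion.** The point holds as a weakness in a stated rule. The one criterion offered for judging random assignment has little power against a gross imbalance confined to one baseline outcome. The 87% to 94% miss rate rests on a 5% level and 5 to 150 roughly independent outcomes, and neither the level nor the number is in the plan. Under the 10% level or the correlations tried, the range is about 70% to 90%, and under correlation much of the apparent gain is false rejection. The documents do not show that any imbalance exists or that an estimate is biased. The gap is that strong per-outcome evidence is collected and no rule uses it. It is worth correcting because the remedy is cheap.

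**What to change.** In section 5.5:
- List the baseline outcomes to be tested and state the significance level.
- Keep the KS test as a global description.
- Add a check of the per-outcome p-values with the Hochberg adjustment already adopted in section 7.4. Compute those p-values so that they respect village clustering and the assignment probabilities, for example by redrawing both stages of the randomisation. As Step 4 shows, adjusting the unclustered LR p-values would flag too often.
- Report each outcome's largest standardised difference between arms with its confidence interval. No fixed margin is proposed, because the documents give no basis for one.

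In sections 7.1 and 7.2, always include the outcome's own baseline value, where it was collected, in the baseline-controlled ITT and CATE models. Adding it only after a failed balance check would make the model depend on a pretest.

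The cost is a few sentences and one table from data already in hand. Some flags will be chance differences, and because the covariate is included regardless, a flag does not change the model.
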